objectives and endpoints	
Primary objectives
 
 
Estimate the attack rate, serial interval, and reproduction number of SARS-CoV-2 infection in peri-urban Maputo.
 
Estimate the proportion of infections that are asymptomatic, and tease out the role these play in transmission.
 
Estimate the incidence rate of SARS-CoV-2 infection, COVID-19 disease (symptomatic infection), rate of severe COVID-19 disease, hospitalization for medical care and mortality, over a 12 month period in peri-urban Maputo
 
Identify risk factors for SARS-CoV-2 infection, for asymptomatic or clinical presentation, and for COVID-19-related death, which could include HIV status, nutritional status, blood group, underlying co-morbidities, household factors, pre-existing levels of anti-alphacoronavirus antibodies (CoV 229E, NL63) or anti-betacoronavirus antibodies (CoV OC43 and HKU1), and availability and adoption of measures aimed to reduce transmission.
 
Create social contact matrices that can be used to parametrize dynamic transmission models.
 
Estimate the household secondary infection rate
 
 
Secondary objectives
 
 
Measure antibody titers over time and analyze the correlation between anti-coronavirus (endemic coronavirus or SARS-CoV-2) antibody titers and reinfection
 
Assess the individual uptake of measures aimed to reduce transmission (quarantine, physical distancing, hygiene, future vaccination) and assess barriers to uptake (absence soap/water, income loss, ability to self-isolate, availability of masks, distrust, lack of understanding of the communication)
 
Derive and validate a clinical prediction rule for SARS-CoV-2 infection.
 
Geographical mapping of clusters, spread and identification of transmission hotspots
 
Sequence selected strains of SARS-CoV-2
 

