analytical methods	
 
* Description of transmission dynamics: rolling incidence rate of COVID-19 disease throughout one year, adjusting for the sensitivity of SARS-CoV-2 RT-PCR on nasal swabs by delay between symptom onset and testing; SARS-CoV-2 infection incidence rate, SARS-CoV-2 annual attack rate, secondary infection rate, and infection fatality risk by age group, by adjusting for the proportion asymptomatics.
 
* Risk factor analysis for SARS-CoV-2 infection and COVID-19 disease, and for severity (hospitalisation), overall and following household transmission in particular.
 
* Model basic and effective reproductive numbers (<math>R_0</math> and <math>R_e</math>), generation time distribution, ratio of transmissibility between symptomatic and asymptomatic cases, duration of the infectious period, household secondary infection rate.
 
* Explore the correlation between <math>R_0</math> and <math>R_e</math>, and the uptake of measures to reduce exposure/ transmission.
 
* Case-cohort, case- control or similar analysis to estimate vaccine effectiveness against confirmed COVID-19 in the population-based surveillance and cohort analysis to estimate vaccine effectiveness against SARS-CoV-2 seroconversion (among sero-survey participants)
 

safety	
The study does not involve an investigational product or intervention

statistical methods	Descriptive (probabilistic) and inferential statistics Negative binomial regression for risk factor analysis Development of a compartmental mathematical model to describe the spread of SARS-CoV-2 on the population level
---------------------	---

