## 2. Study Objectives

### Primary objectives

- Estimate the attack rate, infection fatality, serial interval, and reproduction number of SARS-CoV-2 infection in peri-urban Maputo.
- Estimate the proportion of infections that are asymptomatic, and tease out the role these play in transmission.

- Estimate the incidence rate of SARS-CoV-2 infection, COVID-19 disease (symptomatic infection), rate of severe COVID-19 disease, hospitalization for medical care and mortality, over a 12 month period in peri-urban Maputo.
- Identify risk factors for SARS-CoV-2 infection and for severe COVID-19 disease, which could include reported HIV status, nutritional status, blood group, underlying co-morbidities, household factors, pre-existing levels of anti-alphacoronavirus antibodies (CoV 229E, NL63) or anti-betacoronavirus antibodies (CoV OC43 and HKU1), and availability and adoption of measures aimed to reduced transmission.
- Create social contact matrices that can be used to parametrize dynamic transmission models.
- Estimate the household secondary infection rate

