#### Secondary objectives

- Measure antibody titers over time and analyze the correlation between anti-coronavirus (endemic coronavirus or SARS-CoV-2) antibody titers and reinfection
- Assess the individual uptake of measures aimed to reduce transmission and assess barriers to uptake (absence soap/water, income loss, ability to self-isolate, availability of masks, distrust, lack of understanding of the communication)
- Derive and validate a clinical prediction rule for SARS-CoV2 infection
- Geographical mapping of clusters, spread and identification of transmission hotspots.
- Sequence selected strains of SARS-CoV-2
- Understand non-SARS-CoV-2 etiologies of respiratory disease in the study population.
- Identify factors associated with household SARS-CoV-2 infection and with household infection resulting in Covid19 disease, including viral load and symptoms of household index case, household and individual characteristics and behaviour to prevent infection.
- Estimate total brand-specific vaccine effectiveness (among vaccinees) against PCR confirmed SARS-CoV-2 clinical infection.
- Estimate total brand-specific vaccine effectiveness (among vaccinees) against SARS-CoV-2 seroconversion
- Estimate overall and brand-specific vaccine effectiveness (total among vaccinees and indirect among non-vaccinated) against PCR confirmed SARS-CoV-2

Table 1. Study activities and outcome measures. Primary outcome measures in **bold**.

Planned activities	Sampling strategy and sample size	Outcome measures

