Active syndromic population surveillance (biweekly) with PCR testing of symptomatic individuals – 12 months	15393 individuals (2108 households) Possible cases reporting any respiratory sign or loss of smell or taste, with or without fever, selected for PCR testing. Initially, before widespread community transmission, pooled testing of possible cases; when >50 confirmed cases per week, switch to PCR testing of 1 in 10 possible cases (systematic selection - every 10th possible case)	
 
● COVID-19 disease incidence rate (symptomatic infections per person-month)
 
● COVID-19 related hospitalisation rate
 
● Case (disease) fatality risk (%)
 
● Risk factors for severe outcome/hospitalization
 
● Basic reproduction number
 
● Effective reproduction number
 
● Serial interval
 
● Proportion uptake of measures to prevent infection; barrier uptake
 
● Effectiveness of interventions
 

		
 
• COVID-19 incidence density maps
 
• COVID-19 likelihood ratios of clinical signs
 
• Brand-specific vaccine effectiveness against confirmed COVID-19 (disease)
 

Age-stratified sero-survey at 0, 3, 6, 12 months	2400 individuals/dried blood spot samples per round (800 per age group <18yo, 18-50 yo, >50yo) An age stratified sample of individuals will be selected (simple random sample in each age group)	
 
• SARS-CoV-2 infection annual attack rate (%)
 
• Infection fatality risk
 
• Proportion asymptomatic infections, by age group
 
• Risk factors for infection
 
• Association between antibody titers and reinfection
 
• Brand-specific total vaccine effectiveness against SARS-CoV-2 seroconversion
 
• Overall vaccine effectiveness against SARS-CoV-2 seroconversion
 

Repeated social mixing survey	the same 2400 individuals selected for the sero-survey (800 per age group <18yo, 18-50 yo, >50yo)	
 
• correlation between number of contacts, intensity of contacts and attack rate
 
• correlation between uptake of control measures and attack rate
 
• social contact matrices to be used to parametrize dynamic transmission models
 

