## 7. Statistical Analyses

### 7.1 Methods

All estimated transmission or clinical outcome indicators will be adjusted for the design effect, related to the selection of HDSS enumeration areas (clusters) within the source populations. Intraclass correlation coefficients can be deducted from previous studies in the HDSS. The results of the sero-survey and social mixing survey will additionally be adjusted for age-stratified sampling.

We will calculate a incidence rate of COVID-19 disease throughout one year, adjusting for the sensitivity of SARS-CoV-2 RT-PCR on nasal swabs by delay between symptom onset and testing. Using the longitudinal sero-survey data, determining the proportion of asymptomatics, we will be able to adjust the clinical incidence rate to a SARS-CoV-2 infection incidence rate, and determine the SARS-CoV-2 infection annual attack rate and the infection fatality risk by age group.

We will undertake three risk factor analyses: of SARS-CoV-2 infection, of COVID-19 disease (symptomatic infection), and of COVID-19 hospitalisation and death (severe disease). Using negative binomial regression, we will investigate the association with socio-demographic factors, clinical characteristics such as underlying medical conditions, and uptake of preventive measures. We also investigate the association between SARS-CoV-2 infection (from the sero-survey) and recent exposure, contact and mobility patterns (from the social mixing questionnaire).

We will assume everyone will be susceptible initially and basic and effective reproductive numbers ( $R_0$  and  $R_e$ ) will be calculated by the rate of change of incidence over successive serial intervals (time between onset of infection of index and onset of infection of infected).

We will use established methods (Cauchemez et al 2004; te Beest et al 2013) to estimate generation time distribution, ratio of transmissibility between symptomatic and asymptomatic cases, duration of

the infectious period, and the basic reproduction number, from the transmission data collected in households.

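### The synopsis makes risk factors for symptomatic versus asymptomatic presentation a primary objective; Section 2 omits it, and Section 7.1 plans no such contrast among infected people

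*Combined protocol and SAP*

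**What the plan says.** The risk-factor objective appears in two forms.

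- Synopsis, primary objectives: "Identify risk factors for SARS-CoV-2 infection, for asymptomatic or clinical presentation, and for COVID-19-related death".
- Section 2, primary objectives: "Identify risk factors for SARS-CoV-2 infection and for severe COVID-19 disease". Presentation is not named.

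The analysis text is in Section 7.1: "We will undertake three risk factor analyses: of SARS-CoV-2 infection, of COVID-19 disease (symptomatic infection", with severe disease (hospitalisation or death) as the third. It continues: "Using negative binomial regression, we will investigate the association with socio-demographic factors, clinical characteristics such as underlying medical conditions, and uptake of preventive measures". It does not say whether the disease model is fitted to everyone under surveillance or only to infected people. The analytical methods in the synopsis give a similar list: "Risk factor analysis for SARS-CoV-2 infection and COVID-19 disease, and for severity (hospitalisation), overall and following household transmission in particular".

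Table 1 gives the disease outcome as "COVID-19 disease incidence rate (symptomatic infections per person-month", under the surveillance of all 15,393 residents. It assigns risk factors for infection to the sero-survey, and plans the asymptomatic proportion by age group only.

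A secondary objective comes close to the missing contrast: "Identify factors associated with household SARS-CoV-2 infection and with household infection resulting in Covid19 disease". Table 1 lists it under the investigation of the first 100 households. Section 7.1 gives it no model.

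**The concern.** Presentation is a question about infected people: given infection, who becomes ill? A model of symptomatic disease per person-month asks who, in the whole population, becomes infected and ill. The second mixes two steps, so it cannot answer the first.

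Section 1.1 shows why the distinction matters here. It raises the possibility that host factors and co-morbidities more common in Africa alter whether infection is silent or clinical, and that this in turn affects transmission. If the analyses are run as listed, an association of HIV status, co-morbidity or endemic-coronavirus antibody with disease could come from a different risk of infection, a different risk of symptoms, or both. The plan would have no estimate for the second step outside the household contacts, apart from the proportion by age.

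**Working it through.** **1. The plan's own figures.** Section 7.2 assumes a 40% attack rate, 50% symptomatic and 90% detected. With 15,393 residents:

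- Cases = 15,393 × 0.40 × 0.50 × 0.90 = 2,771. The plan states 2,790, which is 0.7% away.
- Rate = 2,771 / (15,393 × 12) = 1.50 per 100 person-months, as stated. The Poisson 95% interval is 1.44 to 1.56, against the stated 1.45 to 1.56.

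The inputs can therefore be used below. Section 7.2 gives no power for any risk-factor analysis.

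**2. What a population disease ratio measures.** With equal case detection in both groups,

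RR(disease) = RR(infection) × RR(symptoms given infection).

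Take a factor with infection RR 2.0 and no effect on symptoms. Then RR(disease) = 2.0 × 1.0 = 2.0, while the ratio among the infected is 1.0.

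Suppose 20% are exposed (an assumption). The attack rate is 0.40 / (0.8 + 0.2 × 2) = 0.333 in the unexposed and 0.667 in the exposed.

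- Exposed cases: 15,393 × 0.2 × 0.667 × 0.45 ≈ 924.
- Unexposed cases: 15,393 × 0.8 × 0.333 × 0.45 ≈ 1,847.
- SE of the log ratio: √(1/924 + 1/1,847) = 0.040.
- Approximate 95% interval: 1.85 to 2.16, before any design effect.

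So the population ratio would look precise while saying nothing about symptoms.

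**3. What the missing contrast could deliver.** Infections in the sero-survey: 2,400 × 0.40 = 960, of which 480 symptomatic at 50%. Table 4 allows a cut to 1,600 participants, giving 1,600 × 0.40 = 640. Both are upper figures for seroconverters, because people already seropositive at baseline do not count. Infected household contacts would add roughly 600 × 0.17 ≈ 102, using Table 1's 600 contacts and the 17% of Section 7.2.

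Power for 62.5% versus 50% symptomatic (RR 1.25), two-sided 5%, is Φ[(0.125 − 1.96 × se0) / se1], where se0 is the pooled and se1 the unpooled standard error. For 15% exposed among 960, the groups are 144 and 816, se0 = 0.0452, se1 = 0.0440, and power is Φ(0.83) = 0.80. Exposure prevalences are assumptions.

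| Exposed | 960 infections | 640 infections |
|---|---|---|
| 5% | 0.39 | 0.27 |
| 10% | 0.65 | 0.47 |
| 15% | 0.80 | 0.62 |
| 20% | 0.88 | 0.72 |
| 50% | 0.97 | 0.89 |

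These are before clustering, weighting and attrition. An assumed design effect of 1.5 turns 960 into an effective 640, so the right-hand column also serves for that case.

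**4. Symptom misattribution.** Sero-survey rounds are 3 to 6 months apart, and PCR may drop to 1 in 10 possible cases. Symptoms from other causes can therefore be credited to a silent infection. Table 2 expects 8,000 respiratory episodes. If 2,771 of these are COVID-19, the other 5,229 amount to 5,229 / 15,393 = 0.34 per person-year. If they occur at random, the chance of at least one is 1 − exp(−0.34 × 0.25) = 8% over 3 months and 16% over 6 months.

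A true ratio of 1.25 would then appear as (0.625 + 0.375 × 0.08) / (0.5 + 0.5 × 0.08) = 1.21, or 1.18 with 16%. If all 8,000 episodes had other causes, the figures are 12% and 23%, with apparent ratios of 1.20 and 1.16.

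**The case against.** The strongest reply is that total risk of disease is a legitimate target, and that 7.1 sets an infection analysis beside it. A factor with a ratio of 2.0 in both would be recognisable as acting on exposure. This stands in part. However, no comparison is planned, and Table 1 draws infection risk factors from the sero-survey and disease from the full surveillance. The comparison would be informal and without an interval.

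The household objective also stands in part. Contacts are sampled whether or not they have symptoms (Section 4.2), so the contrast can be made there. A reader might infer that symptom development is not studied at all; the household objective and the planned asymptomatic proportion by age do not support that.

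A reader might also infer that the plan will present an exposure factor as a cause of clinical illness. It does not say so: 7.1 speaks of association. That the disease model is population-based is likewise an inference, from the person-month outcome and the count model.

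Another tempting example is a factor that halves infection and doubles symptoms, so that the disease ratio is 1.0. At the plan's 50% symptomatic share, doubling would require every exposed infection to be symptomatic, so it should not be used. A disease ratio of 1.0 would in any case be a correct answer to a different question.

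Finally, restricting to infected people conditions on something the factor may influence, which can introduce selection bias. The added ratio would need that caution too.

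**Conclusion.** The concern holds in limited form. A question that the synopsis calls primary is absent from Section 2 and has no matching analysis in 7.1. If the disease model is population-based, as Table 1 suggests, its ratio cannot answer that question: infection RR 2.0 with no effect on symptoms gives 2.0 against 1.0. This identity assumes equal case detection across exposure groups.

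The contrast can be estimated from data already planned, but with limits. For a ratio of 1.25, power is adequate for common factors and poor for rare ones, and lower again with a sero-survey of 1,600 or with clustering. Misattributed symptoms would pull the ratio towards 1. The point should be corrected before analysis; it does not invalidate the three analyses already listed.

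**What to change.** 1. Reconcile the risk-factor objective in the synopsis with Section 2, stating whether presentation is an outcome.
2. In 7.1, state the risk set of the disease model and, if it is the population, that its ratio combines infection and symptom effects.
3. If the presentation objective stays, add a model of symptomatic versus asymptomatic infection among sero-survey seroconverters and infected household contacts. Log-binomial or modified Poisson regression would do, with household-robust variance and sampling weights.
4. State a rule for attributing biweekly symptom records to the interval in which a person seroconverted, and a sensitivity analysis for misattribution.
5. Note that the ratio is conditional on infection and open to selection bias.

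The cost is one model, one attribution rule and aligned wording, with no new data collection. The price is a smaller sample than the population model, with limited power for uncommon factors and some bias towards 1 from symptom misclassification.

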## Synopsis

design	Prospective cohort study (population-based surveillance and serial sero-survey)
study site & population	
Polana Caniço, peri-urban Maputo, Mozambique: a health- and demographic surveillance site (HDSS) covering a population of approximately 15,393, in the catchment area of the Polana Caniço General Hospital (PCGH).
 
All individuals residing in the 2108 HDSS households for at least 3 months (infants, children, adults, elderly) are included in bi-weekly surveillance rounds, regardless of age.
 
An age-stratified random sample of that population (800 per age stratum) will be selected for the repeated sero- and social mixing survey.
 
No exclusion criteria apply for participants able and willing to provide consent for participation in the study.

duration	December 2020-December 2021 (12 months)

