The transmission potential of SARS-CoV-2 is determined in any particular context by the basic reproduction number ( $R_0$ ) when there is no protective immunity in the population.  $R_0$  will vary with time and context, such as population density, number of contacts and environmental conditions, and is dependent on the period of infectiousness, viral load, and the serial interval. Early data estimated the  $R_0$  for SARS-CoV-2 between 2.0 and 3.4 (Ferretti 2020; Li 2020), higher than that for seasonal influenza (Biggerstaff et al 2014). This is likely in part because of key divergent features from influenza such as pre and asymptomatic SARS-CoV-2 transmission (Ferretti 2020; Kimball 2020; He 2020), near absence of severe disease in young children (Wu et al 2020), and a longer estimated serial interval of 3.96 days (Du Z Emerging Infect Dis 2020). The SARS-CoV-2 average  $R_0$  is also higher than estimated for previous novel viruses, such as influenza H1N1 in the 1918 ( $R_0=1.8$ ) and 2009 ( $R_0=1.6$ ) pandemics (Biggerstaff et al 2014) and SARS-CoV-1 ( $R_0=1-5$ ) (Liu et al 2020).

To date, evidence suggests that in temperate climates between 20 and 50% of infections could be asymptomatic (Mizumoto et al 2020; Bi et al 2020; Kimball et al 2020). Pre-symptomatic shedding is common, with comparable viral load in asymptomatic, pre-symptomatic and clinical cases (Kimball et al 2020). This complicates timely targeted application of interventions since people may not know they are infected and will not behave as if they were. The frequency of asymptomatic infection in sub-Saharan African settings is as of yet unclear, and also may vary by setting. Understanding the proportion of asymptomatic infections and their contribution to the reproduction number is important.

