## 1.2 Rationale

It is recognized that SARS-CoV-2 will transmit differently in African settings, and that risk factors for infection and mild or severe disease may be different to higher income settings. Understanding transmission and identifying at-risk populations is urgent for African countries, who need to target scarce resources as effectively as possible to interrupt transmission and protect vulnerable risk groups.

Box. The epidemiological situation in Mozambique on 29/09/2020.

The SARS-CoV-2 outbreak is still accelerating in Mozambique, as indicated by both the trend in the number of reported cases and the positivity rate. 7983 SARS-CoV-2 infected cases were reported, including 295 imported cases, and 58 deaths. Since the start of the outbreak, 134,011 suspected cases have been tested. In September 2020, consistently more than half of new cases were reported in Maputo City. In Maputo City a total of 3,427 cases and 38 deaths have been reported. The average number of new daily cases reported went from 47 in the first week of September, to 97 in the week up to 26/09. A sero-prevalence survey undertaken in the last two weeks of August 2020, found an overall seroprevalence of 3.8% in Mauto city, with only slight variation between age groups (range 3.0% in 35-59 year olds to 4.5% in  $\geq 60$  year olds). Nevertheless, the latter age group accounts for the majority of hospitalisations. Of all cases reported in Mozambique, 56% were asymptomatic, 37% have a mild symptomatology, 6% moderate symptomatology and 1% a severe symptomatology. 42% of the infected individuals are female.

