### 3. Study Design

Prospective cohort study (observational). We will use the established HDSS to set up population-based COVID-19 surveillance in a household cohort. From any individual in this population reporting any respiratory sign (symptom or lowered peripheral oxygen saturation) or loss of smell or taste, with or without fever, we will collect a respiratory specimen and test these for SARS-CoV-2 virus by PCR, during 12 months. These cases will be identified through bi-weekly household visits, through an alert system involving community leaders and HDSS interviewers, or when presenting with symptoms at healthcare centres or at the referral hospital. Identified healthcare facilities will then alert the study team if a possible case from the HDSS population is consulted or admitted, if the patient agrees. Demographic, epidemiological and clinical data (comorbidities, medication, obesity, HIV, TB, smoking) of possible cases and of the source population will be recorded at baseline; recent illness, potential risk exposure of each household member (including duration and type) to SARS-CoV-2 positive individuals, uptake of measures to reduce exposure/transmission, and barriers to the uptake of such measures, will be

recorded/updated during every household visit. COVID-19 vaccination status will be recorded from possible cases and compared to that of a subset of the population, in a case-cohort design to determine vaccine effectiveness against symptomatic COVID-19.

An age-stratified serial sero-survey will be conducted at baseline in a subset of the population in the population-based COVID-19 surveillance, and at 3, 6 and 12 months, after confirmation of community transmission. Recording vaccination status of all sero-survey participants, we will determine vaccine effectiveness against SARS-CoV-2 seroconversion in a cohort design.

Household transmission will be specifically investigated, by investigating contact history, vaccination status, and the presence of SARS-CoV-2 virus and serology among household members twice during the month after the symptom onset of a household index case.

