An **age-stratified random sample** of that population will be selected for the **repeated sero- and social mixing survey**. By age stratum (0-17 years; 18-50 years; >50 years) we randomly select 800 individuals (simple random sample per age stratum; 2400 in total) from the Polana Caniço HDSS population (regardless of infection or disease status or history), from whom during home visits dried blood spots will repeatedly be collected at 0, 3, 6 and 12 months, vaccination status against COVID-19 will be recorded, and who will be asked to respond to a social mixing questionnaire. A HDSS sampling frame of all individual participants in the HDSS with socio-demographic data and unique identifiers, is available, and will be used to select a simple random sample of individuals by age group.

When a member of a household with no prior widespread transmission (see exclusion criteria) tests SARS-CoV-2 positive, we will revisit the household twice for a household transmission investigation: as soon as possible after the result of the household index case (baseline), and once again one month after symptom onset of the household index case. An initial contact report form will be filled in as soon as possible, ideally within 24 hours, after laboratory confirmation of the primary case in the household. Respiratory and dried blood spot samples will be collected of everyone considered resident (as defined by the HDSS) in the household and who has been in contact with the SARS-CoV-2 positive individual, regardless of age and presence or absence of symptoms. Respiratory samples will be analysed by RT-PCR for SARS-CoV-2 to assess presence of virus and viral load. The dried blood spots for serology on the Luminex assay. Data will be collected on household exposures of contacts and vaccine receipt. Symptomatic household contacts will be tested whenever symptoms appear, as part of the population-based surveillance. This is planned for upto 100 household index cases.

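### Section 7.1 computes R0 from early growth as if nobody were immune, although prior infection is documented and the baseline sero-survey could correct for it; it also defines the serial interval by infection times that surveillance does not observe

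*Combined protocol and SAP*

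**What the plan says.** Section 7.1 opens its account of the reproduction numbers with "We will assume everyone will be susceptible initially". It then says that both R0 and Re are to be "calculated by the rate of change of incidence over successive serial intervals", and explains the serial interval as "time between onset of infection of index and onset of infection of infected". The next paragraph of 7.1 plans a separate estimate of the generation time distribution and of R0 from the household data.

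Three other places bear on this:

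- Section 1.1 ties R0 to the situation "when there is no protective immunity in the population".
- The Box in Section 1.2 says that a survey in late August 2020 "found an overall seroprevalence of 3.8% in Mauto city", with 3.0% to 4.5% across age groups. It describes the outbreak as still accelerating, with average new daily cases rising from 47 to 97 during September.
- Section 3 says "An age-stratified serial sero-survey will be conducted at baseline in a subset of the population", and Section 4.2 says "dried blood spots will repeatedly be collected at 0, 3, 6 and 12 months". The plan is for 2400 people per round, 800 in each of three age strata.

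The Synopsis starts the study in December 2020, while Table 2 in Section 5.1 starts its schedule in October 2020. Both are later than the August survey.

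**The concern.** R0 and Re come from the same quantity, the ratio of incidence over successive intervals. The only thing in 7.1 that turns that ratio into R0 is the assumption that nobody is immune at the start. The protocol's own background contradicts that assumption. If some residents are already protected, the early ratio is an Re that carries the label R0.

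The reproduction number and the serial interval both appear in the first primary objective (Section 2). Section 10.2 plans to present the evolution of the reproduction number to health authorities and the national response team at 3, 6 and 12 months. The Synopsis plans to relate R0 and Re to the uptake of control measures, which presupposes that the two are kept apart.

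The interval wording is a second, separate problem. Time from infection to infection is the generation interval, which 7.1 lists as its own parameter. Surveillance tests people with symptoms (Table 1), so it yields onset dates and not infection dates.

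**Working it through.** The plan states no expected R0 and no precision for it, so there is no planned figure to reproduce.

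**Susceptibility.** Let p be the share protected at the start and S = 1 − p. Early growth estimates R = S × R0. Calling this R0 gives (1 − p) × R0, so the correction factor is 1/(1 − p). The last two columns use the ends of the R0 range cited in Section 1.1 (2.0 to 3.4).

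| p | Source | Reported/true | Factor | True 2.0 reads | True 3.4 reads |
|---|---|---|---|---|---|
| 3.0% | Section 1.2, lowest age group | 0.970 | 1.031 | 1.94 | 3.30 |
| 3.8% | Section 1.2, overall | 0.962 | 1.040 | 1.92 | 3.27 |
| 4.5% | Section 1.2, highest age group | 0.955 | 1.047 | 1.91 | 3.25 |
| 10% | assumed | 0.900 | 1.111 | 1.80 | 3.06 |
| 15% | assumed | 0.850 | 1.176 | 1.70 | 2.89 |
| 20% | assumed | 0.800 | 1.250 | 1.60 | 2.72 |

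As a check, I ran a deterministic renewal model with R0 = 2.0, a population of 15,393, and an assumed gamma interval with mean 3.96 days (the value cited in Section 1.1) and SD 2.0 days. The early estimates were 1.99, 1.91, 1.79 and 1.59 for S = 1, 0.962, 0.90 and 0.80. These match the identity apart from slight depletion of susceptibles.

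**Partial protection.** The table takes every seropositive person as fully protected. If protection is only v, replace p by p × v. With v = 0.5 (assumed):

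- p = 3.8% gives 1/(1 − 0.019) = 1.019
- p = 10% gives 1/(1 − 0.05) = 1.053
- p = 20% gives 1/(1 − 0.10) = 1.111

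**Can S be measured well enough?** With 2400 samples and p = 3.8%, the 95% half-width is 1.96 × √(0.038 × 0.962/2400) = 0.0076, or about ±0.8 points. This is a simple-random-sample approximation that ignores stratum weights, clustering and assay error. Over 3.0% to 4.6%, the factor runs from 1.031 to 1.048. S therefore adds little uncertainty to R0.

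**Interval.** Over one interval of length T at growth rate r, R = exp(rT). Taking the midpoints of the two September weeks as 4 and 23 September (19 days apart, an assumption), r = ln(97/47)/19 = 0.0381 per day. Then:

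- T = 3.96 days gives R = 1.163
- T = 2.96 days gives 1.163 × exp(−0.0381) = 1.120, which is 3.7% lower
- T = 4.96 days gives 1.163 × exp(0.0381) = 1.208, which is 3.9% higher

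An interval that is one day wrong therefore moves R by about 4% in either direction at this growth rate.

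**The case against.** The strongest reply has four parts.

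**The documented effect is small.** A factor of 1.04 is minor beside the 2.0 to 3.4 range in Section 1.1. A reader might infer that R0 will be 10% to 20% too low. The documents do not support that: they give no seroprevalence for the study area at the start, and those values are assumptions. A rise after August is plausible given the September growth, but the August figure is for the whole city and not for the surveillance site.

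**This is not the only R0.** Section 7.1 plans another from household data, and it is the household estimation that the text goes on to feed into the compartmental model. That model may also be fitted to, or validated against, attack rates from the sero-surveys. A reader might infer that the model and its projected intervention effects are biased too. Nothing says that the model starts fully susceptible, so this is possible but not shown. Equally, nothing says that the household estimate or the serology corrects the growth-based R0.

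**Seropositivity is not immunity.** Section 1.1 calls immunity to coronaviruses unclear and raises cross-protection from endemic ones. Dividing by the seronegative fraction alone would swap one fixed assumption for another. This stands, and it is why a sensitivity range is needed.

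**The interval point is partly terminology.** Onset dates are collected, generation time is estimated separately, and an infection-to-infection interval suits an infection incidence series. This stands in part. A reader might infer that both defects push R0 down, but only the susceptibility rule has a direction. A reader might also take the serial interval for a primary outcome measure. It belongs to a primary objective, but Table 1 does not set it in bold.

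**Conclusion.** The rule in 7.1 conflicts with the protocol's own condition for R0 and with its own evidence of prior infection. The growth-based figure is an Re and understates R0 by the share protected at baseline. That is about 4% at the documented 3.8%, if seropositivity protects fully and the August city figure applies. It is less if protection is partial, and more if baseline seroprevalence has risen or if there is protection that the assay does not detect.

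The definition of the serial interval is wrong as worded and cannot be applied directly to symptomatic surveillance data. Any error in R that follows may go either way. Both points are worth correcting because the quantities belong to a primary objective and the data for the correction are already planned.

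**What to change.** Amend Section 7.1 in two places.

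1. Replace the susceptibility assumption with text to this effect: *The growth-based estimate is reported as Re. R0 is derived as Re/S, where S is the susceptible fraction from the month-0 sero-survey, age-weighted to the surveillance population and corrected for assay sensitivity and specificity. The uncertainty in S is carried into the interval for R0. A sensitivity analysis varies the degree to which seropositivity protects.* State also what initial susceptible fraction the compartmental model uses.

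2. Define the serial interval as symptom onset in the index case to symptom onset in the infected contact, and keep generation time for the household model. Say which of the two intervals enters the growth calculation.

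The cost is a few sentences, a little extra analysis and a slightly wider interval for R0. No new data are needed. Table 4 in Section 5.1 warns that the sero-survey may shrink to 1600 people in two age strata. The half-width at 3.8% would then be 1.96 × √(0.038 × 0.962/1600) = 0.0094, or about ±0.9 points, and the age weighting would have to follow the revised strata.
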